| Design | Prospective, one-arm, baseline-controlled pilot study for the evaluation of the VelaShape III combined with UltraShape Power treatment for non-invasive circumference reduction to the thighs. | | | | |
| Study Population | Up to 40 healthy adult volunteers seeking noninvasive circumference reduction of thighs. Male and females, 18 to 60 years of age enrolled at up to two investigational sites. | | | | |
| Treatment and Duration | Eligible subjects will receive 3 bi-weekly treatments to the thighs at 2-week intervals, with the VelaShape III and UltraShape Power devices according to the study protocol. Each subject will return for 3 follow up visits: four weeks (4wk FU), 8 weeks (8wk FU) and 12 weeks (12wk FU) after the last treatment (Tx.3), for total expected study duration of 16 weeks. | | | | |
| Objective | The objective of this trial is to evaluate the safety and efficacy of the VelaShape III combined with UltraShape Power for circumference reduction of the thighs. | | | | |
| Primary Objective | Statistically significant circumference reduction post combined VelaShape III and UltraShape Power treatments at 12 weeks follow-up (12wk FU) versus baseline. Evaluate the safety of the combined treatment with the VelaShape III and UltraShape Power devices. | | | | |
| Secondary Objectives | Circumference reduction post combined treatments Pre-Tx.2, Pre-Tx.3 and all follow-up visits (4wk FU, 8wk FU and 12wk FU) versus baseline. Statistically significant reduction post combined treatment at the follow-up visits only. Investigator satisfaction assessment will be performed independently, using a 5-point Likert scale questionnaire, at each follow-up visit (4wk FU, 8wk FU and 12wk FU). Subject satisfaction assessment will be performed independently by the subject, using a 5-point Likert scale questionnaire, at each follow-up visit (4wk FU, 8wk FU and 12wk FU). Comfort level during treatment: Comfort assessment will be performed independently by the subject using a 10-point NSR scale. The subjects will answer this questionnaire regarding each device separately and combined after each treatment (Tx.1, Tx.2 and Tx.3). | | | | |
| Efficacy Endpoints | Primary and secondary objectives will be assessed using the following efficacy endpoints: | | | | |

| SYNERON CANDELA | Pilot Study to Evaluate VelaShape III & UltraShape Power Combined Treatment for Thigh Circumference Reduction | | | d Treatment for | |

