|-----------------|--|----------|-----------|-----------------|----------------------------|
| Confidential | Protocol # | DHF24451 | Rev. Date | October 6, 2017 | Page 7 of 39 |

| | Circumference measurements of the treatment area |
|---------------------|---|
| | 2. Investigator satisfaction |
| | 3. Subject satisfaction |
| | 4. Pain assessment |
| | 5. Photography |
| | |
| Safety Endpoints | Number, severity and type of any adverse events recorded throughout the study and |
| | post treatment (immediate and delayed response). |
| Statistical Methods | Descriptive statistics will be used to present changes in the assessments along the study |
| | course. Circumference measurements and subject assessments' and satisfaction data |
| | will be analyzed using two-tailed Wilcoxon Signed Rank test and/or paired t-test |
| | (alpha=0.05) to analyze the data difference from baseline and longitudinal change. |

INTRODUCTION AND RATIONALE

Background

Adipose tissue is a loose type of connective tissue specialized to store lipids. The majority of lipids stored in adipose cells are triglycerides formed from imported free fatty acids and glycerol. It is not uniformly distributed in the body. The major adipose depot is subcutaneous (about 80% of all body fat). In men, it normally represents 15-20% of body weight and in women, 20-25% of body weight. A certain amount of body fat is necessary for normal female reproduction and health. Subcutaneous adipose tissue helps to shape, cushion and insulate the body and provides padding to some organs.

Liposuction is a procedure that can help sculpt the body by removing unwanted fat from specific areas. ^{2,3,4} The increasing popularity of this procedure is associated with the evolution of techniques and equipment for fat removal, body reshaping and cellulite treatments. Besides the traditional suction-assisted lipoplasty, other options include ultrasound-assisted and external ultrasound-assisted liposuction, power-assisted liposuction and laser lipolysis, as well as low-level laser-assisted liposculpture.⁵

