Up to 40 healthy subjects from up to two investigational sites will be enrolled in this study. All subjects will undergo an assessment of their general health. All subjects will receive treatment for circumference reduction with VelaShape III combined with UltraShape Power for the thighs. Eligible subjects will receive 3 bi-weekly treatments, at 2-week intervals, to thighs with the VelaShape III combined with UltraShape Power devices. Each of the three treatments (Tx.1, Tx.2 and Tx.3) include the following steps, as shown in Table 2.

Table 2: Combined Treatment by area

| Step | Thigh Treatment |
|------|--|
| 1 | VelaShape III (VContour applicator to inner thigh) – 10 minutes at time on |
| | temperature |
| 2 | VelaShape III (VSmooth applicator to lateral thigh) 10 minutes at time on |
| | temperature |
| 3 | Ultrashape Power to inner and outer thighs – FTZs applied per User Guide |

The subject will return for 3 follow up visits: four weeks (4wk FU), 8 weeks (8wk FU) and 12 weeks (12wk FU) after last treatment (Tx.3). The total expected study duration for each subject is 16 weeks.

At baseline and before each treatment (Tx.1, Tx.2 and Tx.3) and at follow-ups (4wk FU, 8wk FU, 12wk), the subject's weight, circumference and fat thickness (using caliper) will be measured. Photography will be performed under visible light conditions of the front, right and left sides of the thighs.

After each treatment (Tx.1, Tx.2 and Tx.3), the comfort assessment will be performed by the subject using the NSR scale. The subjects complete the questionnaire regarding each device separately and combined.

In addition, at each follow-up visit (4wk FU, 8wk FU, and 12wk FU), the subject and investigator questionnaires will be completed.

OBJECTIVE

The objective of this trial is to evaluate the safety and efficacy of the VelaShape III combined with UltraShape Power for circumference reduction of the thighs.

| SYNERON (CANDELA) Pilot Study to Evaluate VelaShape III & UltraShape Power Combined Treatm Thigh Circumference Reduction | | | | d Treatment for | |
|---|------------|----------|-----------|-----------------|-----------------------------|
| Confidential | Protocol # | DHF24451 | Rev. Date | October 6, 2017 | Page 12 of 39 |

Primary Endpoint

- 1. Statistically significant circumference reduction post combined VelaShape III and UltraShape Power treatments at 12 weeks follow-up (12wk FU) versus baseline.

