- 2. Number, severity and type of adverse events following combined treatment with the VelaShape III and UltraShape Power devices (immediate and delayed response), as recorded throughout the study.

Secondary Endpoints

- 1. Circumference reduction post combined VelaShape III and UltraShape Power treatments at Pre-Tx.2, Pre-Tx.3 and all follow-up visits (4wk FU, 8wk FU and 12wk FU) versus baseline. Statistically significant circumference reduction post combined treatment at the follow-up visits only.
- 2. Investigator satisfaction assessment will be performed independently, using a 5-point Likert scale questionnaire, at each follow-up visit (4wk FU, 8wk FU and 12wk FU).
- 3. Subject satisfaction assessment will be performed independently by the subject, using a 5-point Likert scale questionnaire, at each follow-up visit (4wk FU, 8wk FU and 12wk FU).
- 4. Comfort level during treatment: Comfort assessment will be performed independently by the subject using a 10-point NSR scale. The subjects will complete this questionnaire regarding each device separately and combined after each treatment (Tx.1, Tx.2 and Tx.3).

[figure not shown]
STUDY POPULATION

Number of Subjects

This study will enroll and be comprised of up to 40 subjects, who meet all the inclusion and none of the exclusion criteria, from up to two investigational sites. The subject will receive treatment for circumference reduction of thighs.

Subject Withdrawal and Replacement

Subjects enrolled in the study can discontinue their participation at any time for any reason without prejudice or reduction in the quality of their medical care. The investigators or sponsor can terminate a subject's participation in this study to protect the subject's health or if the subject fails to follow directions resulting in noncompliance to study procedures. Subjects who withdraw or are terminated from the study may be replaced to ensure at least 60 subjects have completed the study. Subjects who fail to complete the treatment may be replaced and will not be evaluable.

Inclusion Criteria

A subject is eligible to participate in the study if he/she meets all the following inclusion criteria:

- 1. Signed informed consent to participate in the study.
- 2. Female and male subjects, \geq 18 and \leq 60 years of age at the time of enrollment.
- 3. Fitzpatrick Skin Type I to VI.
- 4. Fat thickness of at least 1.5 cm (measured by calibrated caliper).

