During copying the treatment area to the transparent template, the following signs will be marked on transparency according to the following table (Table 4):

Table 4- Marking the intended area to be treat by UltraShape

| Step | Thigh Treatment |
|------|---|
| 1 | The thigh area will be marked on the transparency. Each thigh (left |
| | and right) will be marked separately. |
| 2 | Mark the Subject's identification code on the transparency for each |
| | thigh (left and right) separately. |
| 3 | Define the thigh (right or left) on the transparency. |
| | Separate transparency for each side. |

At the subsequent treatment sessions, this transparent template will be placed according to these signs on the treated area, and the line of treatment area will be re-marked.

Marking height circumference and circumference measurement

Patients should stand up straight when arms are placed at the rear of the neck and the head is positioned towards the horizon. Elbows will be positioned in front of the body (Figure 4).

[figure not shown]

Figure 4: Body positioning during marking height for circumference measurements

The height of midsection will be measured using the height measuring device (supplied by Syneron Candela). The marking pencil will be placed horizontally at the edge of the measurement device during the marking procedure (Table 5).

Table 5- Thigh Circumference Measurements

| St | tep | ٨ | Measurement |
|----|--|---|---------------------------------------|
| 1) | Mark the midsection for circumference (=Midline) measurement for left and right thighs separately. | | Moline CI O 2-3cm C3 O Treatment Area |

Confidential

 Protocol #
 DHF24451
 Rev. Date
 October 6, 2017
 Page 19 of 39

| St | tep | Measurement |
|----|---|-------------|
| 2) | The height for the circumference measurement will be marked for each thigh separately. | |
| 3) | Measure the circumference of each thigh separately with the Circumference Measuring Tape. | |

For each treatment area, the measurements will be taken at 2 cm above midsection (=2cm above Midline) measurement and 2 cm below midsection (=2cm below Midline) measurement.

The height of the midsection thigh (will be used as a reference for all study visit measurements) and the circumference measurements will be recorded in the CRF.

VelaShape - General Treatment Procedure

[figure not shown]
- 1. Ensure that the subject is in a comfortable position for the procedure.

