- Pregnancy inquiry prior to each treatment and at the final follow-up visit, a urine pregnancy test will be performed for women with child-bearing potential.

DATA ANALYSIS

Recording

All data will be recorded on site source documents and transcribed onto Case Report Forms (CRFs). The site will be monitored by Syneron staff or designees to assure adherence to the clinical trial requirements, subject safety, protocol procedures, and for data accuracy. The Case Report Forms and images will be reviewed and retrieved during the monitoring visit. All source documentation will remain in the subject's files at the site.

Review and Analysis of all data collected will be conducted by the Sponsor or designee as described for this protocol with the following data:

Demography and Baseline Measurements

Demographic and baseline/screening measurements (e.g., weight, height and digital images) will be collected and descriptively presented.

Treatment Visit

[figure not shown]
Skin assessment by the PI, photographs of the treated region, and pain scores will be collected used to document any adverse events to assess the device performance.

Follow-up Visit Measurements

Follow-up measurements for weight, circumference and digital images will be used for comparative measurements with their respective measurement at baseline. Primary endpoints will be evaluated 12 weeks post last treatment (Tx.3). Secondary endpoints may be evaluated at all visits.

Safety

Safety of device procedure will be evaluated through skin assessments by the PI and research staff. The occurrence and severity of all complications from the start of the study will be recoded.

Protocol Revisions and/or Deviations

Except for emergency situations, no changes or deviations in the conduct of this protocol will be permitted without the prior approval of the Sponsor.

The IRB/IEC that granted original approval for the study must be notified of all changes in the protocol, and will approve any change or deviation that may increase risk to the subject, and/or that may adversely affect the rights of the subject or validity of the investigation.

In the event of an emergency, the Investigator will institute any medical procedures deemed appropriate. However, all such procedures must be promptly reported to the sponsor and the IRB/IEC.

ADVERSE EVENTS (AE)

An adverse event (AE) is any adverse change in health or side effect that occurs in a study participant during their participation in the study.

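### The replacement rule aims for at least 60 completers, but enrolment is capped at 40, so the target cannot be reached even with no loss

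*Combined protocol and SAP*

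**What the plan says.** The enrolment limit appears three times in the combined protocol and SAP, always as 40:

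- Table 1, Study Synopsis, Study Population: "Up to 40 healthy adult volunteers seeking noninvasive circumference reduction of thighs".
- Study Design Overview: "Up to 40 healthy subjects from up to two investigational sites will be enrolled in this study".
- Study Population, Number of Subjects: "This study will enroll and be comprised of up to 40 subjects".

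The next subsection, Subject Withdrawal and Replacement, says that subjects who withdraw or are terminated "may be replaced to ensure at least 60 subjects have completed the study". It then adds: "Subjects who fail to complete the treatment may be replaced and will not be evaluable".

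The synopsis describes a one-arm study. The documents contain no sample-size rationale: no power, effect size, standard deviation or expected loss. Nothing says whether replacement subjects count towards the 40.

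**The concern.** The protocol gives two incompatible sizes for one study. The replacement sentence works as an operating rule, since it names the number of completers that replacement is meant to secure. Read literally, that number is never reached under the cap. A sponsor who pursues 60 breaches the enrolment limit stated in three places; one who respects the limit misses the stated minimum.

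The number of subjects behind the 12-week circumference result depends on this rule, because subjects who do not finish treatment are declared not evaluable. With no sample-size calculation to fall back on, nothing else in the documents settles how many completers the primary efficacy result should rest on. The two sizes also give different precision for the efficacy and safety endpoints.

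**Working it through.** **Inputs.** Enrolment cap 40 (synopsis, Study Design Overview, Number of Subjects). Completer target 60 (Subject Withdrawal and Replacement). Two-sided alpha 0.05; the synopsis says circumference data "will be analyzed using two-tailed Wilcoxon Signed Rank test and/or paired t-test". The documents give no loss rate, so the values of d below are assumptions.

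**Can 60 be reproduced?** Maximum completers = 40 × (1 − d).

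| Assumed loss d | Completers from 40 enrolled | Enrolment needed for 60 completers, 60/(1 − d) |
|---|---|---|
| 0% | 40 | 60 |
| 5% | 38 | 64 |
| 10% | 36 | 67 |
| 20% | 32 | 75 |
| 30% | 28 | 86 |

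At zero loss the shortfall is 60 − 40 = 20, and 20/60 = 33%. The target is 60/40 = 1.5 times the cap.

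**Other readings of the two numbers.**

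- Per arm: there is one arm.
- Per site: the 40 is given as a total over up to two sites.
- Thighs: the rule counts subjects, and 40 subjects would give 80 thighs.
- Replacements outside the cap: replacing each lost subject by one other restores at most 40 completers. Reaching 60 would need added subjects who replace nobody.

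**What separates 40 from 60 (illustration).** Assume exactly 40 or 60 analysed subjects and one paired difference per subject. The second assumption is needed because Table 5 says "Measure the circumference of each thigh separately with the Circumference Measuring Tape", the text below it sets two measurement levels, and nothing says how these values become one per subject. No SD is given, so results stay in SD units.

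| Quantity | n = 40 | n = 60 |
|---|---|---|
| Effect detectable with 80% power, paired t-test (noncentral t) | 0.454 SD | 0.368 SD |
| 95% CI half-width, t(0.975, n − 1)/√n | 0.320 SD | 0.258 SD |
| Detectable effect, Wilcoxon signed rank, effective n = n × 3/π, normal data | 0.465 SD | 0.377 SD |

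The interval is 0.320/0.258 = 1.24 times as wide at 40, that is 24% wider. An effect of 0.368 SD, which has 80% power at 60, has 62% power at 40 (0.621 exact; 0.624 by simulation with 200,000 runs).

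**Safety.** The Data Analysis section says: "The occurrence and severity of all complications from the start of the study will be recoded". The natural denominator is therefore subjects treated. For an adverse event seen in nobody, the one-sided 95% upper bound is 1 − 0.05^(1/n): 7.2% with 40 treated and 4.9% with 60 treated.

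**The case against.** The strongest reply is that this is a one-arm pilot with no stated power, that replacement is optional, and that no success criterion, analysis set or stopping point refers to the 60. On this view a missed target triggers nothing. That limits the consequence, but it does not make the target attainable: optional replacement still cannot deliver a minimum of 60 from 40.

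A second reply is that three statements of 40, one of them in the dedicated subsection, against a single 60 suggest that the 60 is a stray figure. That is plausible, but it is inference; nothing in the text proves it.

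A third reply is that the power and precision figures only show what sample size does in general, and that 40 is a ceiling and not a planned number. This is fair, and the figures should be read as illustration. The safety bounds also apply per number treated. Reaching 60 completers with any loss would mean treating more than 60, and replacements outside the cap could take the number treated above 40.

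Finally, the claim that the target will be missed holds only if the cap binds. One-for-one exchange is the natural meaning of replacement, although the rule does not spell it out. If the cap is the erroneous number, the target itself may be sound. The contradiction remains in either case.

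**Conclusion.** The concern holds. With the 40-subject cap in force, the stated completer minimum is unreachable by at least 20 subjects, one third of the target, whatever the retention. This needs only the two stated numbers and the ordinary meaning of replacement. The differences in power and interval width rest further on one difference per subject and on exactly 40 or 60 being analysed; the Wilcoxon figures also assume normal data.

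The error should be fixed before the protocol is relied on, but it is not fatal to a pilot. The documents leave open which number is wrong.

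**What to change.** The sponsor should reconcile the two numbers.

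- **If the cap of 40 is intended:** restate the completer figure in Subject Withdrawal and Replacement, and say in the same sentence whether replacements count inside the 40. If they are additional, the figure can be at most 40. If they count inside it, the figure should be lower and based on a stated expected loss, for example 36 at an assumed 10% or 32 at an assumed 20%. The cost is one corrected sentence and a less favourable stated number of completers.
- **If 60 completers are intended:** correct the cap in the synopsis, the Study Design Overview and Number of Subjects. Enrolment would need to be at least 60, or 67 at an assumed 10% loss and 75 at 20%, if replacements count within the new enrolment number. The cost is three text changes and more subjects to recruit and treat.

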The subject will review the informed consent form and the study will be explained to the subject including all risks, potential benefits, procedures, visit requirements, and other alternative treatment options. If the subject qualifies and wishes to participate they will complete the ICF with a signature and date. The original will be retained with subject's records and a copy will be provided to the subject.

The following measurements will be performed and recorded at the specified times throughout the study (Table 3).

Table 3- Clinical Evaluation Measurements and Tools

| Measurement | When to conduct | Method |
|----------------------------------|--|---|
| Height | Baseline | Scale |
| Weight | | Scale |
| BMI |] | Calculation |
| Circumference | Prior to all treatments and at all follow- | Standardized circumference measuring tape |
| measurements | ups visits (Tx.1, Tx.2, Tx.3. 4wk FU, 8wk | Standardized circumference measuring tape |
| Fat thickness: Caliper | FU and 12wk FU) | Caliper |
| measurement | | Camper |
| Photographs | | Standardized digital photographs |
| Urine pregnancy test | Prior to each treatment, and at the last follow-up visit (Tx.1, Tx.2, Tx.3, 12wk FU) | Urine pregnancy test |
| Pregnancy inquiry | At each visit (at treatments visits- prior to treatment) | Pregnancy inquiry |
| Treatment-associated pain | Immediately after treatment (Tx.1, Tx.2, Tx.3) the subject will be asked to assess the pain level during treatment | Numerical Scale Response (NSR) |
| Immediate Response Assessment | Immediately after treatment the investigator should assess the post-treatment immediate response | Post-treatment Side Effect Severity Scale (Table 9) |
| Subject satisfaction | At all follow-up visits: 4wk FU, 8wk FU | Subject Satisfaction Questionnaires (Table 10, Table 11) |
| Investigator satisfaction | and 12wk FU | Investigator Satisfaction Questionnaire (Table 10) |
| Safety | During treatment and throughout study | Examination of skin in the treated area, interview subjects, Adverse Events form, Occurrence and Severity Ratings, as well as relation to treatment, action taken and outcome |

| SYNERON © CANDELA | Pilot Study to Evaluate VelaShape III & UltraShape Power Combined Treatment for Thigh Circumference Reduction | | | | |
|-------------------|--|----------|-----------|-----------------|-----------------------------|
| Confidential | Protocol # | DHF24451 | Rev. Date | October 6, 2017 | Page 16 of 39 |

[figure not shown]

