Appendix III - Pain assessment) for each treatment phase:

- a. VelaShape III
- b. UltraShape Power
- 2. Clinical effects All visible and palpable immediate response will be recorded for the entire treatment area using a 4-point severity scale (Table 9).
- 3. Safety aspects will be assessed before and after each treatment:
 - a. Adverse Events Record the number, severity and type of any adverse event occurring before, during and after treatments.
- 4. Subject will also be provided with the following instructions for care of the treated areas in the informed consent form.
 - a. Temporary skin erythema (redness) and edema (swelling), as well as heat and tightening sensations, may occur up to a few hours after the treatment, but normally do not last longer. If the subject feels significant discomfort longer than that time, cool/cold compress (but not ice packs) may be applied for relief. Overthe-counter pain medication such as Tylenol may be used.
 - b. On the evening after the treatment, subjects should wash the treated areas gently with lukewarm water and avoid very hot or cold water in these areas. Generally, subjects may use their regular soaps after treatment, as long as these are not scrub soaps or exfoliants.
 - c. The treated areas should also not be exposed to potential mechanical damage (e.g., kickboxing, massage) at least 48 hours post-treatment.
 - d. Tanning of any sort (sun exposure, tanning beds, and artificial sunless tanning lotions) is not allowed in the treated areas during the entire course of the study since it might cause hyperpigmentation.
 - e. Subjects will be instructed to use a high factor sunscreen with SPF of at least 30 and to protect the treated areas from direct sunlight for the entire period of the study.

[figure not shown]
Return Visits

All subjects will be requested to return to the clinic at the following time-points during the study to assess the clinical performance of the device:

- Visit 4: FU1 4 weeks (±7 days) post last treatment.
- Visit 5: FU2 8 weeks (±7 days) post last treatment.
- Visit 6: FU3 12 weeks (±7 days) post last treatment.

At each return visit the following procedures will be conducted and data recorded:

Weight.

- Caliper measurements.
- Circumference measurements.
- Photographs as conducted at baseline visit.
- Completion of study questionnaires:
 - o Investigator satisfaction using the 5- Point Likert Scale.
 - Subject satisfaction using the 5- Point Likert Scale.

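### Anyone who does not complete treatment is declared not evaluable whatever the reason, so the one-arm 12-week circumference result covers treatment completers only

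*Combined protocol and SAP*

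**What the plan says.** The rule is in Study Population, Subject Withdrawal and Replacement: "Subjects who fail to complete the treatment may be replaced and will not be evaluable". That paragraph lets subjects leave at any time and for any reason. It adds: "The investigators or sponsor can terminate a subject's participation in this study to protect the subject's health".

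The data at issue are these:
- **Primary efficacy endpoint:** a statistically significant circumference reduction at the 12-week follow-up versus baseline, in one arm. The synopsis names a two-tailed Wilcoxon signed rank test and/or paired t-test at alpha 0.05.
- **Secondary circumference:** Pre-Tx.2, Pre-Tx.3 and every follow-up visit. Significance is asked for at the follow-up visits only.
- **Comfort:** "The subjects will complete this questionnaire regarding each device separately and combined after each treatment (Tx.1, Tx.2 and Tx.3".
- **Safety:** Table 3 schedules it "During treatment and throughout study", and the Data Analysis section records all complications from the start of the study.

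On follow-up, Return Visits says "All subjects will be requested to return to the clinic at the following time-points during the study" and lists "Visit 6: FU3 12 weeks (±7 days) post last treatment".

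No section defines an all-treated set, a missing-data method or a sensitivity analysis. Case Report Forms asks only that missing data be explained.

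On numbers, the section states "This study will enroll and be comprised of up to 40 subjects", and the withdrawal paragraph states "Subjects who withdraw or are terminated from the study may be replaced to ensure at least 60 subjects have completed the study".

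**The concern.** The evaluability rule depends on something that happens after treatment starts. A subject who stops because of pain, a burn or disappointment is treated the same as one who moves away. Pain and second-degree burns are listed as anticipated effects, so stopping for tolerance is foreseeable. In a one-arm trial no comparator shares the selection, and replacement restores the count of completers without restoring the people who left.

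The 12-week mean reduction and its significance test would then describe only those who tolerated and persisted with three sessions. Comfort data raise a related question: a subject who stops because the initial session hurt has already given a score, and the plan does not say whether that score is kept.

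**Working it through.** The plan gives no sample-size derivation, SD, effect size or dropout rate, so there is no stated figure to reproduce. Everything below except the 40, the 60, the two-sided 0.05 level and the three-session course is assumed, to show scale.

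**1. Hand check.** Let a share d of treated subjects stop, with mean reduction k times that of completers. The all-treated mean divided by the completer mean is (1 − d) + d·k, and the overstatement is the reciprocal minus 1.
- k = 0: 5.3% (d = 5%), 11.1% (10%), 25.0% (20%). Example: 1/0.90 − 1 = 11.1%.
- k = 0.5: 2.6%, 5.3%, 11.1%.
- k = 1: 0%.

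**2. Simulation of stopping that depends on early response.** There were 2,000,000 subjects per setting. True mean reduction is 1.0 cm; SD of change 1.0, 1.5 or 2.0 cm; early and 12-week change are bivariate normal with correlation 0.3, 0.5 or 0.7. The odds of stopping double for each SD less early reduction. With 40 treated, completers number 38, 36 or 32. Bias in standard errors is bias/(completer SD/√n). The chance of a significant reduction when there is no true change is the upper tail of a noncentral t with that noncentrality; the nominal value is 2.5%.

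| Stopping | Completer mean (true 1.0 cm) | Bias in SE | Significant reduction, no true change |
|---|---|---|---|
| 5% | 1.01-1.05 | 0.06-0.15 | 2.9-3.5% |
| 10% | 1.02-1.10 | 0.12-0.29 | 3.3-4.7% |
| 20% | 1.04-1.18 | 0.22-0.52 | 4.0-7.3% |

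Check of one entry: at 10%, SD 2.0 and correlation 0.7, the bias is 0.095 cm. The standard error is about 2.0/√36 = 0.333, and 0.095/0.333 = 0.285. The simulated 0.288 is slightly higher because completers have a slightly smaller SD. If stopping is unrelated to response, every bias is zero.

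**3. What no-change imputation does.** With a true mean of 1.0 cm it gives 0.92-0.99 at 10% stopping, so it lowers the estimate. It does not repair the test. If q is the completing share, m the completer mean and s their SD, adding zeros gives a mean of q·m and, when m is near zero, an SD of about √q·s. Then t = q·m/(√q·s/√N) = m·√(qN)/s, which is the completer t. Simulated with no true change and correlation 0.7, upper-tail rejection is 4.5% for both analyses at 10% stopping, and 7.2% (completer) versus 7.1% (imputed) at 20%. At 10% and SD 1.0 cm the two estimates are 0.046 and 0.042 cm: both lie above the true zero.

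**4. Comfort.** Assume a completer mean of 4 after Tx.1 and 10% stopping. If stoppers average 6, the all-treated mean is 0.9 × 4 + 0.1 × 6 = 4.2; if 8, it is 4.4; if 4, it is 4.0. A completer-only table shows 4.0 each time.

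**5. Follow-up date.** The synopsis, Study Design Overview and Follow-up Visit Measurements put Tx.3 in parentheses after the last treatment. Return Visits and Table 8 say only the last treatment. The two agree for anyone who has all three sessions; for an early stopper the date is not settled.

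**6. Numbers.** At most 40 enrolled cannot yield at least 60 completers. At 5-20% stopping, 40 enrolled give 38 to 32 completers, and 60 completers need 60/0.95 = 63.2, so 64, up to 60/0.80 = 75 enrolled.

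**The case against.** Several objections have force.

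- **The three-session course is part of the endpoint.** The 12-week visit is counted from Tx.3, so the effect in those who had the full course is a legitimate pilot question. This stands as a reason to keep the completer analysis, but not to make it the only one.
- **The bias is small and its mechanism assumed.** At 5-10% stopping it is a fraction of a standard error, and the documents support neither a rate nor a link to response. This stands and limits the weight of the point.
- **The secondary data carry low stakes.** Pre-Tx.2 and Pre-Tx.3 have no significance criterion and comfort has no success threshold. This also stands.

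A reader might infer that the rule definitely discards comfort scores and pre-treatment circumference from early stoppers. The documents do not support that. The sentence does not say collected data are dropped; the Data Analysis section speaks of reviewing and analysing all data collected, and uses pain scores to help document adverse events. The text is ambiguous.

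A reader might also infer that adverse events in early stoppers go uncounted. The safety text points the other way. Because the evaluability sentence is not limited to efficacy, a clarifying line is needed, but no exclusion is stated.

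Finally, the two ways of timing follow-up might be read as a contradiction. They are not: the early stopper is simply a case left unaddressed.

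**Conclusion.** The point holds and should be fixed. As written, the one-arm 12-week circumference result covers treatment completers only, and no section restores the others. The fate of their earlier circumference and comfort data is unclear. The direction favours the devices only if stopping is related to tolerance or response. Under the assumed model, the size is 0.06-0.29 standard errors at 5-10% stopping and up to 0.52 at 20%; it is zero if stopping is unrelated to response.

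It is tempting to conclude that the completer result and a no-change imputation bracket the true value. That holds only for the assumed positive effect. With no true change both estimates err in the same direction and the t-test is almost unchanged.

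The conflict between 40 enrolled and 60 completed is a separate defect in the same section. It does not depend on any assumption, and it adds no weight to the evaluability point.

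**What to change.** Replace the evaluability sentence so that:
1. The safety set is every subject who received any study treatment, replaced or not, with discontinuations listed by reason.
2. Comfort and the Pre-Tx.2 and Pre-Tx.3 circumference are summarised for all treated subjects with data, including those who later stop or are replaced.
3. The 12-week circumference is reported for all treated subjects with a baseline and available follow-up, stating the numbers treated, completed and missing. The completer analysis is shown alongside as the estimate for the full three-session course.

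A no-change imputation may be added as a descriptive, more conservative estimate of the mean. It should not be presented as correcting the false-positive rate or as bracketing the truth. Using available follow-up does not remove bias from subjects who never return, which is why the missing counts and reasons matter.

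State the date from which follow-up is timed for subjects who stop before Tx.3. Separately, reconcile the enrolment limit with the completer target, and say whether replacements count toward the limit.

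The cost is protocol wording, slightly more analysis, and follow-up visits for early stoppers who agree to return. The circumference and comfort estimates may become slightly less favourable.
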